### **8.1.6 Time to Progression**

Time to progression is defined as the time from the date of first selumetinib dose until date of documented objective disease progression by ICR per REiNS criteria.

### **8.1.7 Time to Response**

Time to response is defined as the time from date of first selumetinib dose until the date of first documented objective response (which is subsequently confirmed), by ICR per REiNS criteria.

### **8.1.8 Clinical Outcome Assessments**

A COA is any assessment that may be influenced by human choices, judgment, or motivation and may support either direct or indirect evidence of treatment benefit. Clinical outcome assessments can be reported by a participant (PRO), a clinician (ClinRO), an observer (ObsRO), or through a performance-based assessment ([FDA-NIH BEST Resource](#)). A COA may be used in clinical studies to provide either direct or indirect evidence of treatment benefit. It is important to examine the impact of therapy on symptoms, function, and other health-related QoL of the participant to aid understanding of the risk-benefit profile.

A PRO is one type of COA and is a general term referring to all outcomes and symptoms that are directly reported by the participant. Patient reported outcomes have become important in evaluating the effectiveness of study interventions in clinical studies and will aid in understanding of the benefit/risk evaluation ([EMA Guideline 2016](#), [FDA Guidance for Industry](#)).

The following PRO instruments will be administered in this study:

- Pain Intensity Plexiform Neurofibroma (PAINS-pNF)
- Pain Interference Index Plexiform Neurofibroma (PII-pNF)
- Patient reported Outcomes Measurement Information System (PROMIS physical function items)
- Plexiform Neurofibromas Quality of Life Measure (PlexiQoL)
- Paediatric Quality of Life Inventory (NF1 module acute Version 3.0 – adult report) Skin Sensations domain
- EuroQol 5-Dimension 5-level (EQ-5D-5L)
- Patients Global Impression of Change (PGIC)
- Patients GLOBAL Impression of Severity (PGIS)

Patient Reported Outcomes will be administered according to the SoA.

The ECOG performance status will also be assessed as a COA in this study.

Patient reported outcomes data collection will be discontinued after the participant discontinues study intervention.

#### **8.1.8.1 PAINS-pNF**

The use of an NRS-11 measure is well established for measuring pain intensity ([Atkinson et al 2010; Dworkin et al 2005; Wolters et al 2013; Wolters et al 2016](#)). Pain intensity is considered a core concept that is important to assess in the NF1 population ([Wolters et al 2013](#)). The REiNS International Collaboration, after assessing PRO measures for pain in patients with NF1, recommended the NRS-11 for use in the assessment of pain intensity in patients aged  $\geq 8$  years ([Wolters et al 2016](#)). This measure was found to be both reliable and valid, and it is preferred over other measures such as the Visual Analogue Scale and the Faces Pain Scale-Revised because of its psychometric properties and wide use in clinical research ([Wolters et al 2013](#)). However, there is no NRS-11 measure specifically validated for patients with NF1-PN. To address this gap, the NCI is currently going through the qualification process with the PAINS-pNF Scale ([FDA Drug Development Tool](#)). The NCI is willing for its qualitative work to be used in support of the PAINS-pNF measure to be used in the proposed Phase III study in adult NF1-PN participants.

For this study, the PAINS-pNF which is a ‘fit for purpose’ measure for NF1-PN patients that is based on an NRS-11 scale will be used. The PAINS-pNF has 2 items, one assessing participants’ experience of spikes of PN-related pain intensity (also known as episodic tumour pain), which are defined as sudden bursts of tumour pain that may occur spontaneously or in response to a stimulus and the other item is their experience of chronic PN-related pain intensity (also known as usual tumour pain), which is defined as tumour pain that is present most of the time, both for a target PN-location. Participants report pain intensity by selecting the number/integer from 0 (no tumour pain [spike]/no tumour pain [usual/chronic]) to 10 (worst tumour pain possible [spike]/worst tumour pain possible [usual/chronic]). In the event that a participant taking part in the study had a target PN resection and remained in the study, PAINS-pNF data will continue to be collected.

A copy of the scale is provided in [Appendix G 1](#).

#### **8.1.8.2 PII-pNF**

The PII-pNF assesses the extent to which PN pain interferes with daily functioning. All items ask the participant to consider the pain related to their PN in the past 7 days. Participants are asked how much their PN pain has made it hard for them to engage in physical activities (eg, challenging physical activities, self-care), affected their physiological processes (eg, sleep, energy) or impacted their social-emotional functioning (eg, enjoyment of activities,

mood). Items are rated on a 7-point Likert scale (0 = not at all to 6 = completely), and the total score is the mean of the completed items.

A copy of the scale is provided in Appendix [G 2](#)

#### **8.1.8.3 Pain Medication Assessment Diary**

##### **Pain Medication e-Diary**

At the screening visit, the site staff will pre-populate the e-Diary on the handheld device with the pain medications that the participant uses for chronic PN pain, as well as any medications that they typically use for spikes of PN pain.

On a daily basis the participant will record on the e-Diary the pain medications that they have taken for their chronic PN pain and spikes of PN pain.

The participant should bring their handheld device to each site visit; the site staff will review if any changes need to be made to the pre-populated medications on the device.

##### **Investigator Assessment of Pain Medication**

At the frequency stipulated in the SoA, the investigator will record in the eCRF if the participant's analgesic requirement has changed compared to baseline since it was last assessed. This assessment will be made based on discussions with the participant and knowledge of any changes in their pain management. If the investigator determines that there has been a change, they will record if there has been an increase or decrease and the reason for this change.

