- p The PN assessments will be performed at screening and every 4 cycles ( $16 \pm 1$  weeks) up to Cycle 24 (ie, at Cycle 4, 8, 12, 16, 20, and 24). After 24 cycles, PN assessments will be performed every 6 cycles ( $24 \pm 1$  weeks) as long as the participant remains on study intervention. If an unscheduled assessment is performed (eg, to investigate clinical signs/symptoms of progression) and the participant has not progressed, the subsequent assessments at the next scheduled visit must be performed. All volumetric MRI scans should be performed relative to Cycle 1 Day 1, ie the time course should not change if the participant experiences a dose interruption or there are delays in previous scan visits.
- q PAINS-pNF scores and PN pain medication should be collected on the daily e-Diary during screening, the intervention period and up to EoT. Chronic target PN pain intensity PAINS-pNF scores must be recorded for at least 4 days out of 7 days for at least 2 weeks during the screening period for a participant to be considered eligible for study.
- r Participants will complete a daily drug diary during the interventional period to record whether study intervention was taken as instructed.

s The investigator will record in the eCRF if the participant's analgesic requirement has changed compared to baseline since it was last assessed. Assessments will be performed at site visits with additional telephone assessments at Cycle 3, Day 28; Cycle 5, Day 28; Cycle 7, Day 28; Cycle 9 Day 28 and Cycle 11 Day 28 (see [Table 2](#)).

t PGIC 1 'since your last visit to the study site' should be assessed at site visits Cycle 1, Day 28; Cycles 2, 4, 6, 8, 10, 12; PGIC 2 'since starting the study medication' should be assessed at Cycle 12 or EoT if the participant discontinues pre-Cycle 12.

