Following the identification of the strongest drug class in chronic PN pain medication at each cycle, the change in score at each cycle compared to baseline will be programmatically identified following the algorithm outlined in Figure 3. If changes in the strongest drug class from baseline do not follow under the categories of Figure 3. of “Increased” or “Decreased,” the category “No Change” will be assigned. For the cycles where no PN chronic medication has been recorded in the eDiary, the change will be set to “Missing”.

A secondary definition for change from baseline in PN pain medication (Increased/Decreased/No Change) is derived using the investigator analgesic requirement assessment recorded on the e-CRF, indicating whether the reason is PN pain or other pain.

Figure 3: PN Pain Medication Score Changes Algorithm

PN, plexiform neurofibroma; WHO, World Health Organisation.

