4.2.9.2 Derivations

Detailed derivations for PAINS-pNF chronic target PN pain intensity average cycle score is defined in Section [4.2.2.1.2](#).

An increase in eDiary-reported chronic PN pain medication per cycle compared to baseline is defined as one of the following:

Primary definition: Increase from baseline ≥ 1 point (increase to a stronger class of analgesic medication on the WHO modified analgesic ladder [see Section [3.3.8](#), Table 2]) with the same drug of the strongest score taken for at least 3 days in a 28-day cycle (refer to Section [3.3.8](#),

- [Figure 3](#)).
- Sensitivity definition 1: Increase from baseline ≥ 0.5 point (increase to a stronger class of medication on the WHO modified analgesic ladder [see [Section 3.3.8 Table 2](#)] or an increase in the daily dose or number of pain medications within the same analgesic class) with the same drug taken for at least 3 days in a 28-day cycle (refer to [Section 3.3.8](#),

- [Figure 3\)](#)
- Sensitivity definition 2: “No increase in PN pain medication at a specific cycle compared to baseline” will be identified as those patients who had available eCRF data on investigator assessment of analgesic requirement but did not have an investigator’s assessment of “increased” analgesic requirement “due to PN pain”.

Following the definitions in Section [4.2.9.1](#), chronic target PN pain palliation values will be 1 for patients experiencing pain palliation and 0 for patients that do not.

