4.2.11.2 Derivations

For both spike and chronic PN pain medication, the analgesic ladder class and the strongest analgesic ladder score for each cycle will be derived following the scoring algorithm presented in Section 3.3.8. For chronic PN pain, changes from baseline (Increased/Decreased/No Change) will also be derived as outlined in Section 3.3.8.

At each cycle, a binary variable will be derived, set to 1 if a decrease in chronic PN pain medication is observed as per definition in Section 3.3.8 and 0 otherwise. A sensitivity definition of this binary endpoint is derived using the secondary definition of decrease from baseline as assessed by the investigator when the reason for the decrease in analgesic requirement is PN pain.

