4.2.11.6 Additional Analyses of Pain Medication

Descriptive analyses of chronic PN pain medication will be produced for the FAS as follows:

- Strongest analgesic ladder category and score at baseline and at each post-baseline cycle,
- A shift table with medication that “increased,” “decreased,” or “No Change” as compared to baseline at each cycle,

Descriptive analyses of spike PN pain medication will be produced for the FAS as follows:

- Strongest analgesic ladder category at baseline and each post-baseline cycle.

Chronic and spike PN pain medications will be listed.

For the investigator assessment of pain medication during the randomised period, descriptive analyses of the number of patients whose medication “increased,” “decreased,” or “No Change” as compared to baseline at each cycle will be shown. The number of patients whose pain medication increased or decreased will also be shown separately by reason.

The analyses on PN pain medication, change in PN pain medication and PN pain medication decrease during the randomised period (except for spike medication) will be repeated for patients in Pain FAS.

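### The investigator's analgesic question names two reference points, but the SAP scores every answer as change from baseline, so a site that answers for the interval would have a sustained increase scored as no increase

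*Protocol*

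**What the plan says.** Protocol 8.1.8.3 (Investigator Assessment of Pain Medication) has the investigator record in the eCRF whether the participant's "analgesic requirement has changed compared to baseline since it was last assessed". Footnote s of the Schedule of Activities repeats the phrase word for word. If a change is judged to have occurred, "they will record if there has been an increase or decrease and the reason for this change". No analgesic level is recorded under this item.

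On timing, footnote s says "Assessments will be performed at site visits with additional telephone assessments at Cycle 3, Day 28", with further calls in Cycles 5, 7, 9 and 11. The scheduled site visits supply the other cycles up to Cycle 12.

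The SAP uses the answers as follows.

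- **Section 3.3.8:** "A secondary definition for change from baseline in PN pain medication (Increased/Decreased/No Change) is derived using the investigator analgesic requirement assessment".
- **Section 4.2.9.2, sensitivity definition 2 for palliation:** patients with no increase at a cycle are "identified as those patients who had available eCRF data on investigator assessment of analgesic requirement but did not have" a rating of increased requirement due to PN pain.
- **Section 4.2.11.2:** the sensitivity version of the medication-decrease variable is "derived using the secondary definition of decrease from baseline as assessed by the investigator", where the reason is PN pain.
- **Section 4.2.11.6:** counts of patients whose medication rose, fell or stayed the same "as compared to baseline at each cycle will be shown".

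Section 4.2.11.4 bases the investigator analyses on observed records. No section says how a run of answers is to be combined.

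**The concern.** The phrase can be answered in two ways. One answer compares today's requirement with baseline. The other says whether anything has changed since the previous visit or call. A participant who stepped up analgesia in an earlier cycle and is still on the higher regimen is *increased* on the first reading and *no change* on the second. Because only direction and reason are recorded, a single record does not show which reading the investigator used.

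The protocol keeps these two references apart elsewhere. The Patient Global Impression of Change is asked once relative to the last site visit and separately relative to the start of study medication (Protocol 8.1.8.7 and footnote t).

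The no-increase condition in the palliation definition is there to stop pain relief obtained through stronger analgesia from counting as a treatment response. Under SAP 4.2.9.2, a continuing increase answered as *no change* is not treated as missing. It meets the condition. Time to palliation takes the first qualifying cycle, so under sensitivity definition 2 one misclassified cycle can create an event or bring one forward, provided the pain score has also improved enough.

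**Working it through.** The plan gives no figure on this point to reproduce. The check sets the item's two readings against the SAP's scoring rule.

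**Inputs**

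- Assessments: at least one investigator record in each of Cycles 1 to 12 (site visits plus the Cycle 3, 5, 7, 9 and 11 calls; Schedule of Activities and Table 2).
- Scoring: each cycle's record is read as change from baseline (SAP 3.3.8). Any available record other than *increased* due to PN pain counts as no increase (SAP 4.2.9.2).
- Assumption for illustration: one record per cycle, and a single step-up for PN pain in cycle k, held to Cycle 12.

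**Sustained increase**

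Cycles truly above baseline = 12 − k + 1 = 13 − k. On the interval reading only cycle k is flagged, so cycles scored as no increase = (13 − k) − 1 = 12 − k. On the baseline reading all 13 − k cycles are flagged and none is misclassified.

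| Step-up in cycle k | Cycles above baseline | Flagged, interval reading | Scored as no increase | Share |
|---|---|---|---|---|
| 1 | 12 | 1 | 11 | 91.7% |
| 2 | 11 | 1 | 10 | 90.9% |
| 3 | 10 | 1 | 9 | 90.0% |
| 6 | 7 | 1 | 6 | 85.7% |
| 9 | 4 | 1 | 3 | 75.0% |
| 12 | 1 | 1 | 0 | 0% |

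**Step-down that does not go below baseline**

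Take a step-up of two levels in Cycle 3 and a step-down of one level in Cycle 8, still above baseline through Cycle 12. On the baseline reading, Cycles 3 to 12 are all *increased*. On the interval reading, Cycle 3 is *increased*, Cycle 8 is *decreased*, and the other eight of those ten cycles are *no change*. If PN pain is the recorded reason, SAP 4.2.11.2 counts Cycle 8 as a decrease from baseline although the participant is above it. A full return to baseline gives the same false decrease.

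**Would carrying an increase forward repair collected data?**

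Suppose a site answered relative to baseline and recorded *increased, increased, no change, no change*. That is a correct account of a return to baseline in the third cycle. Carrying the increase forward until a recorded decrease would rescore the last two of the four cycles as *increased*, and both would be wrong. Even where the interval reading was used, direction-only answers cannot always recover the status after a partial reversal: in the example above, *increased* then *decreased* does not show whether the participant is at baseline or still above it.

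**The case against.** The strongest reply is that the sentence does name its comparator, baseline, and that the remaining words can be taken as the period under review. The SAP uses baseline consistently, so the two documents agree on the intended reference. On that reading no carry-forward is needed, and its absence is not a separate gap. The eCRF page is not among the documents. Its item text and completion guidance may settle the matter, and nothing supplied shows that any site answered for the interval.

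This limits the point but does not remove it. The harm is conditional. The route to misclassification is still open, because the protocol text can be read either way and the SAP has no safeguard if it is read the other way.

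The reply is also right about reach. Palliation needs the pain-score improvement as well: at least 2 points, or the psychometric threshold in sensitivity 5, which applies only if that threshold differs from 2. The palliation result has other checks, since sensitivities 1 and 4 use the eDiary. The SAP's main medication model is eDiary-based and the investigator version is a repeat of it. Decreases for reasons other than PN pain are not counted.

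**Conclusion.** The wording is ambiguous, and the SAP relies on one reading without securing it. Where a site answers relative to the last assessment, a sustained increase for PN pain is scored as no increase in 12−k of 13−k cycles, and a step-down for PN pain that ends at or above baseline counts as a decrease. Where sites answer relative to baseline, the error is zero. The true extent lies between these and cannot be judged from the documents, which give neither the eCRF wording nor how often analgesia changes. The direction of any bias between arms is also unknown.

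Affected are palliation sensitivities 2 and 5, time to palliation under sensitivity 2, the investigator-based repeat of the decrease model, and the by-cycle descriptive tables.

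A reader might infer that most investigator records are wrong, or that the pain results as a whole are in doubt. The documents support neither. The 9-in-10 figure describes one hypothetical participant under the less favourable reading; it is not an error rate for the trial. The response rate, the main analyses of PAINS-pNF and PlexiQoL, and the primary palliation definition do not use this item, and nothing affected is in the multiple testing procedure.

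**What to change.** Delete the words that refer to the last assessment in Protocol 8.1.8.3 and footnote s, and align the eCRF completion guidance, so that each visit or call asks for the current requirement against baseline. This is a wording change.

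The item is collected only up to Cycle 12, so the edit cannot help participants already past that point. For records already collected:

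1. Before unblinding, establish from the eCRF wording and from site practice which reference was used.
2. Cross-check the answers against the concomitant-medication entries (reason, dates, dose and frequency; Protocol 6.5) and the daily medication eDiary.
3. State the outcome in the SAP. Do not apply a blanket carry-forward rule, because it would rescore correct answers from sites that used baseline.
4. If the reference cannot be established, report the investigator-based analyses with that limitation stated.

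The cost is a short protocol and guidance edit, one sentence in the SAP and a blinded data review. The review is the larger part of the work.

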#### **8.1.8.4 PROMIS**

The Adult PROMIS Physical Functioning (PF) items scales measure self-reported capability rather than actual performance of physical activities. Items assess upper extremity function (dexterity), lower extremity function (walking or mobility), and central regions (neck, back) as well as activities of daily living such as running errands.

Participants will be assessed using selected items from the PROMIS item bank that map to physical function concepts relevant to patients with symptomatic PNs.

A copy of the scale is provided in Appendix [G 3](#).

#### **8.1.8.5 PlexiQoL**

The PlexiQoL is a patient-derived QoL measure specific to adults with NF1-associated PNs. It assesses the impact of PNs on patients' ability to fulfil their human needs. The scale adopts the needs -based model of QoL and joins a large portfolio of high-quality outcome measures that are widely used in international clinical trials ([Heaney et al 2020](#)).

The measure consists of 18 dichotomous items with 0 = "Not True" and 1 = "True". Scores are summed to a maximum of 18, with lower scores indicating better quality of life.

A copy of the scale is provided in Appendix [G 4](#).

#### **8.1.8.6 PedsQL (NF1 Module Acute Version 3.0 – Adult Report) Skin Sensations Domain**

The adult version of PedsQL™ NF1 Module can be used to understand the multidimensional nature of NF1 on the HRQoL patients with this disorder and may assist in medical decision making. The instrument demonstrates initial feasibility, reliability, and discriminant validity. The PedsQL™ NF1 Module 3.0: Adult self-report instrument comprises 18 domains/subscales and participants will be assessed using the Skin Sensations domain (3 items) with a 7-day recall period ([Nutakki et al 2013](#)).

These are rated on a 5-point Likert scale from 0 (Never) to 4 (Almost always). Items are reversed scored and linearly transformed to a 0 to 100 scale as follows: 0 = 100, 1 = 75, 2 = 50, 3 = 25, 4 = 0. Domain scores are calculated by the sum of all the items over the number of items answered.

A copy of the scale is provided in Appendix [G 5](#).

#### **8.1.8.7 PGIC and PGIS**

The global impressions of change for PN-related pain are self-reported measures that will be used to assess change in participant's PN-related pain as follows:

- PGIC 1: 'since your last visit to the study site'
- PGIC 2 'since starting the study medication'

The 2 PGICs will be used to evaluate the clinical significance of changes in PN-related spikes of pain and chronic pain on a 7-point scale (1 = Very much improved to 7 = Very much worse) ([Guy 1976](#)).

The global impression of severity for PN-related pain is a self-reported measure used to assess severity of participant's PN-related pain. It is a global two-item measure and will be used to evaluate the clinical significance of PN-related spikes of pain and chronic pain severity on a 4-point scale (1 = No pain to 4 = Severe).

Copies of the scales are provided in Appendix [G 6](#) (PGIC) and Appendix [G 7](#) (PGIS).

